##### Lost to follow-up

All attempts must be made to contact a patient who is lost to follow-up. Patients who are lost to follow-up should be formally discontinued from the study on the day of the last unsuccessful attempt at contact.

##### Notification and practical modalities

At a minimum, for any patient who discontinues the study, the patient status must be completed in the CRF. When a patient discontinues prior to study completion, all applicable activities scheduled for the final study visit should be performed at the time of discontinuation. In particular, patients are required to return the Cefaly® Abortive Program device.

[figure not shown]

Figure 1 - Study flowchart

## 5. Subjects

The study will randomize at least 600 patients, men or women, in a 1:1 ratio into each group (verum or sham).

### 5.1. Inclusion criteria

The following inclusion criteria apply:

- 1) Age from 18 to 65 on the day of signing the informed consent form
- 2)  $\geq$  1-year history of migraine with or without aura according to the diagnostic criteria listed in ICHD-III beta (2013) section 1, migraine (8), with the exception of aura without headache, hemiplegic migraine and brainstem aura migraine
- 3) Migraine onset before the age of 50
- 4) Having between 2 and 8 moderate or severe migraine attacks (Grade 2 or 3) per month in each of the two months prior to screening
- 5) Patient understands the study procedures, alternative treatments available, and voluntarily agrees to participate in the study by giving written informed consent
- 6) Patient is able to read and understand the written information (instruction sheet, paper diary and AE reporting form)

## 6. Medical device and treatment

### 6.1. Description of the device under investigation

The device under investigation is the Cefaly® Abortive Program device. It is a small, portable product, which is meant to be worn on the forehead by attachment to a self-adhesive electrode. A rechargeable battery provides power to the Cefaly® Abortive Program device. The device acts by external stimulation of the upper branch of the trigeminal nerve (e-TNS). The Cefaly® Abortive Program device generates very precise electrical impulses to trigger action potentials on supraorbitalis and supratrochlearis nerve fibers.

The Cefaly® Abortive Program device (Figure 2) is comprised of the following specifications:

- Dimensions: 55 mm x 40 mm x 15 mm
- Weight: 12 g.

Figure 2 - Cefaly® Abortive Program device

The Cefaly® Abortive Program device is connected to the body via a self-adhesive electrode (Figure 3) applied on the forehead. The Cefaly® electrode is 94 mm long and 30 mm high. It makes the interface between the Cefaly® Abortive Program device and the skin. This electrode has been approved by the FDA.

Figure 3 - Cefaly® electrode

According to the randomization, the patients will use a specific verum or sham Cefaly® Abortive Program device, that is programed to perform a unique 2-hour treatment session.

#### 6.1.1. Verum device

The Cefaly® Abortive Program verum device will be programed with the following parameters: rectangular biphasic pulse current (100 Hz, 250  $\mu$ s) at a linearly increasing intensity starting at 0 mA up to a maximum of 16 mA after 14 minutes, then remaining stable for the rest of the session (106 minutes).

#### 6.1.2. Sham device

The Cefaly® Abortive Program sham device will be programed with the following parameters: rectangular biphasic pulse current, with similar pulse width (250  $\mu$ s), at a linearly increasing intensity sufficient for the patient to feel strong paraesthesia similar to that produced by the verum device, but with a different frequency that will not induce a sedative effect to the central nervous system (1).

#### 6.1.3. Blinding

The sham device is identical in shape and color as the verum device. Also, the sham device will beep and flash identically to the verum device. No differences will exist between the sham and verum devices and it won't be possible for the patient as for the investigator to know which device is verum or sham. The only difference will be in the stimulation parameters.

Blinding between verum and sham stimulations has been validated by a test at Spincontrol Laboratory (Tours, France) on 128 subjects (62 received verum and 66 received sham) who were unable to distinguish between the verum and the sham stimulation.

## 6.2. Device technology

The Cefaly® Abortive Program device is an external cranial neurostimulator designed for supraorbital neurostimulation (also known as external trigeminal nerve stimulation: e-TNS). Trigeminal nerve stimulation induces a sedative effect on the central nervous system (1), that causes headache pain relief during migraine attacks.

The Cefaly® Abortive Program device generates electrical impulses that are transmitted transcutaneously via a bipolar self-adhesive electrode placed on the forehead.

The Cefaly® Abortive Program device operates on direct electrical energy, which is output from one rechargeable battery.

The device is a constant current generator for a maximum skin impedance of 2.2 k $\Omega$  that delivers rectangular biphasic symmetrical pulses with a zero electrical mean. The impulses and generator characteristics allow insignificant overshoot and mismatch. The pulse width corresponds to the chronaxie of targeted supraorbitalis and supratrochlearis nerves. The frequency used in the current study for the

verum device is 100 Hz. The sham device has a different frequency that will not induce a sedative effect to the central nervous system (1).

The supraorbital electrode is designed in order to cover both sides of the supratrochlearis and supraorbitalis nerves, which are branches of the trigeminal nerve (Figure 4).

The electrical impulses generated by the Cefaly® Abortive Program device are transmitted transcutaneously via the supraorbital electrode to excite (trigger action potentials) the supratrochlearis and supraorbitalis nerves. Supratrochlearis and supraorbitalis (or supratrochlear and supraorbital) nerves belong to the upper branch of the trigeminal nerve (V1). Therefore, the supraorbital neurostimulation is also known as external trigeminal nerve stimulation (e-TNS).

[figure not shown]

Figure 4 - The Cefaly® electrode placed on the forehead covers the supratrochlearis and supraorbitalis nerves

### 6.3. Mechanism of action

The Cefaly® Abortive Program device generates electrical impulses. Electrical impulses get out of the device via 2 metallic contacts. Contacts are in connection with 2 conductive areas on the self-adhesive electrode. The self-adhesive electrode is applied on the forehead. Therefore, electrical impulses generated by the Cefaly® Abortive Program device are running through the metallic contacts then through the electrode in order to carry out excitation on the nerve fibers just located under the forehead skin i.e. supratrochlearis and supraorbitalis (or supratrochlear and supraorbital) nerves which belong to the trigeminal nerve. Consequently, electrical impulses generated by the Cefaly® Abortive Program device trigger signals (action potentials) on supratrochlear and supraorbital nerves or trigeminal nerve. Repetitive excitation of trigeminal nerve is a neuromodulation of the trigeminal system. Neuromodulation with high frequencies of the trigeminal system induces a sedative effect on the central nervous system and a trigeminal nociceptive threshold modification, that causes headache pain relief during migraine attacks.

## 6.4. Training test devices

During the recruitment phase, the patient will have to perform him/herself a 20-minute training test session to check his/her ability to use the device appropriately. This training test session will be performed using a specific training test device.

Compared to the treatment device (Cefaly® Abortive Program device), the training test device has a shorter session duration (20 minutes instead of 120 minutes). The ramp-up and ramp-down times are the same and the stimulations parameters are identical. The training test device has a grey button (Figure 5) while the treatment device has a dark pink button. This prevented confusion in device handling.

Figure 5: Training test (left) and treatment (right) device used during the trial.

According to the randomization, the patients will use a specific verum or sham training test device, that is programed to perform a unique 20-minute training test session.

## 6.5. Use during the trial

Indications for use: abortive treatment of migraine with or without aura in patients 18 years of age or older.

The patient will apply the training test device (verum or sham) for a first 20-minute training test session to check his/her ability to bear the paresthesia feeling (absence of forehead skin allodynia) and to use the device appropriately. Then, at home, the patient will apply the Cefaly® Abortive Program device (verum or sham) for a 120-minute treatment session during a qualifying migraine attack. Duration, intensity and/or interruption will be recorded for each patient thanks to a built-in electronic system in the device.

## 6.6. Medication during the trial

Patients will be instructed NOT to take any anti-migraine rescue medication during the 2-hour treatment phase. Medication intake during the 2-hour treatment phase will be considered as a protocol violation. After the 2-hour treatment phase, if and only if the patient has moderate or severe migraine headache pain (Grade 2 or 3), he/she is allowed to take his/her own anti-migraine rescue medication. Use of rescue

medication will be recorded by the patient in the diary for the 24 hours following the beginning of the treatment.

If the patient has a migraine prophylactic treatment, any modification of this migraine prophylaxis treatment is NOT allowed. Change in prophylactic treatment will be considered as a protocol violation.

## 6.7. Device provisioning

The sponsor will deliver all the investigational devices and related accessories directly to the investigators. A unique randomization number will be allocated to each patient. Each unique randomization number corresponds to either the verum or the sham group and is associated with one kit of two devices: a training test device and a Cefaly® Abortive Program (treatment) device. Consequently, for a given patient, the training test and Cefaly® Abortive Program devices are both verum or both sham, according to the randomization. A single sealed kit containing the training test device and the Cefaly® Abortive Program device, both with the same allocated randomization number, will be delivered to each patient, so that they cannot be reused on different patients. For each patient, the unique randomization number indicated on the kit has to be reported in the patient's CRF and will allow to identify, at the end of the study, which devices were used by each patient, and thus whether the patient used verum or sham devices.

Investigational clinical devices are to be dispensed only in accordance with the protocol. The investigator is responsible for keeping accurate records of the clinical supplies received from the sponsor, the amount dispensed and returned, and the amount remaining at the conclusion of the study.

## 7. Practical study modalities

### 7.1. Efficacy outcome measures

The treatment efficacy outcomes will be assessed based on the following clinical data.

- **Headache pain severity.** In order to evaluate the modification of pain severity from baseline to 2-hour and 24-hour time points, patients will be asked to note their headache pain intensity on the following scale: 0 = no pain; 1 = mild pain; 2 = moderate pain; 3 = severe pain.
- **Migraine-associated symptoms.** The patient will also note the presence of migraine-associated symptoms (photophobia, phonophobia, nausea, vomiting) and will specify which associated symptom is the most bothersome symptom (MBS) at baseline.
- **Rescue medication intake.** The patient will also record whether he/she took ANY anti-migraine rescue medication during the 24 hours following the beginning of the e-TNS treatment session.

The following table depicts when the different measures will be made:

	At baseline, i.e. just before the beginning of the e-TNS session	2 hours after the beginning of the e-TNS session	24 hours after the beginning of the e-TNS session
Headache pain severity	•	•	•
Migraine-associated symptoms	•	•	•
Identification of the most bothersome migraine-associated symptom (MBS)	•		
Rescue medication intake			•

All clinical data will be collected on a paper diary and AE reporting form.

### 7.2. Blinding

The investigator and patient will be blinded from whether the allocated devices are verum or sham.

The treatment allocation will be concealed using the following procedure. Verum and sham devices will be programmed by the manufacturer CEFALY Technology. They will be sent to each investigator by blocks with equal number of verum and sham kits of devices. The only indication on the kit of devices will be a unique randomization number. The list of correspondence between allocation (verum or sham) and randomization number (also named as randomization code) will be provided in a sealed envelope to the coordinating investigator. This procedure ensures a blinding from the enrolling investigator as well.

In case of an emergency, identification of a specific blinded investigational device can be revealed without breaking the blind for the remaining devices. In this case, the investigator should contact CEFALY Technology that will provide the required identification details.

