### 4.2. Experimental protocol

Patients will be recruited from the research site database and advertising or during a standard care visit at the headache clinic/research site or at an on-demand appointment. They will be screened during a visit at the investigation site (headache clinic or research site).

Inclusion and exclusion criteria will be reviewed, and the eligible patients will be randomized and then trained about the practical use of the Cefaly® Abortive Program device (device handling, electrode placement, etc.). Following that training, they will perform themselves a first 20-minute e-TNS training test session with a verum or a sham training test device to control their ability to use the device appropriately and bear the feeling of the stimulation.

Included patients (who meet all of the study criteria) will be provided with study material (a Cefaly® Abortive Program (treatment) device with accessories and paper documents) for 2 months to be used on an outpatient basis as soon as they experience a moderate or severe migraine headache (Grade 2 or 3).

The overall study flowchart is illustrated in Figure 1. During the different phases the investigator will monitor adverse events (AE).

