#### 8.2.1. Sample size

The sample size was computed based on the primary outcome, i.e. pain freedom at 2 hours. The sample size should allow detecting a statistically significant difference between the treatment (verum) and control (sham) outcome value with a power of at least 90% and a 5% level of significance.

In the pilot clinical trial, the pain freedom at 2 hours associated with the Cefaly® Abortive Program treatment was 35.4%. Results from previous randomized, sham-controlled trial using a stimulation device (transcranial magnetic stimulator) as acute treatment of migraine reported 22.0% of pain freedom at 2 hours in the sham group (11).

A power analysis showed that a sample of 239 patients per group allows detecting a statistically significant difference between the treatment (35.4%) and control (22.0%) pain freedom at 2 hours with a power of at least 90% and a 5% level of significance.

Taking into account a rate of 20% of patient loss during the study (based on the pilot clinical trial), at least 299 patients should be included in each group. Consequently, 600 patients will be included in the present clinical investigation.

NOTE: The sample size meets the FDA definition of Phase III clinical investigation (according to the FDA, a clinical investigation can be considered as a Phase III clinical study when the number of participants ranges from 300 to 3,000 volunteers who have the disease or condition).

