### 8.2.3. Statistical methods

- All relevant general, safety and efficacy data will be descriptively summarized at each time point.
- Continuous data will be summarized by the number of subjects (N), the arithmetic mean, the standard deviation, the coefficient of variation as a percentage (CV%), the median, the inter-quartile range, the minimum and the maximum value, when appropriate.
- Categorical data will be summarized by absolute (N) and relative (%) frequency tables.
- Where considered as relevant, the study data will also be graphically depicted.
- For each patient, the outcomes will be calculated according to all data available, and if necessary, imputation of missing data will be performed according to the last value carried forward method.
- Unless otherwise stated, all statistical tests will be conducted at the  $\alpha=0.05$  (2-sided) level.
- Comparison between two independent samples (verum and sham group) will be performed using either the Mann-Whitney U test (also called the Mann-Whitney-Wilcoxon (MWW), Wilcoxon rank-sum test, or Wilcoxon-Mann-Whitney test), the Fisher test or the Anova test.

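### Kits are blocked by site but no planned comparison is stratified by site, which forgoes a little precision and leaves consistency across sites unseen

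*Combined protocol and SAP*

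**What the plan says.** Section 4.1 describes a multicenter trial. On the supply of kits, section 7.2 states: "They will be sent to each investigator by blocks with equal number of verum and sham kits of devices". Under section 4.2.1 the investigator takes a sealed, numbered kit for each patient. Neither the block size nor the order in which kits are used is given.

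For the analysis, section 8.2.3 states: "Comparison between two independent samples (verum and sham group) will be performed using either the Mann-Whitney U test", with the Fisher test and the Anova test as the alternatives. Section 8.2.4 adds the modified intention-to-treat (mITT) conditions and a carry-forward rule. No section names site as a stratum, covariate or random effect, or plans a look at results by site. The sample size in section 8.2.1 is an unstratified comparison of two proportions.

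On recruitment, section 4.2 states: "Patients will be recruited from the research site database and advertising or during a standard care visit at the headache clinic/research site".

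**The concern.** When allocation is balanced within groups of patients, the analysis would normally use those groups. If response differs between sites, a test that ignores site counts those differences as random error, although balanced allocation has largely removed them from the comparison of arms. The test then rejects less often than its nominal level and forgoes some precision on both primary outcomes.

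Site differences are plausible. Patients arrive by several routes, and each site trains its own patients, judges the training session against exclusion criterion 14 and reviews the diary at the final visit. The plan also offers no way to see whether an effect comes from all sites or only a few, which matters for a trial presented as Phase III evidence.

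**Working it through.** **1. The plan's own figure.** Inputs from section 8.2.1: verum 35.4%; sham, from a published trial that "reported 22.0% of pain freedom at 2 hours in the sham group"; and the target "with a power of at least 90% and a 5% level of significance". Section 8.2.3 makes the level two-sided. With mean rate (0.354 + 0.220)/2 = 0.287:

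n = [1.960·√(2·0.287·0.713) + 1.282·√(0.354·0.646 + 0.220·0.780)]² / 0.134² = (1.254 + 0.811)² / 0.01796 ≈ 237.4, so 238.

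The plan has "a sample of 239 patients per group", so the figure reproduces within rounding. With 20% loss, 239/0.80 = 298.75, so 299 per group and 600 in total, as stated.

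**2. Why pooling is conservative.** Take no treatment effect and a mean rate of 22.0%. The pooled test uses the variance 0.220·0.780 = 0.1716. With arms balanced within site, the true variance is smaller by the variance of the site rates. The documents do not give the spread between sites, so assume normal site effects on the logit scale. At SD 0.8, numerical integration with the mean held at 22.0% gives a variance of site rates of 0.0165. The ratio is 1 − 0.0165/0.1716 = 0.904. The actual type I error is 2·[1 − Φ(1.960/√0.904)] = 2·[1 − Φ(2.06)] ≈ 3.9%. Random loss of 20% disturbs the balance a little, and simulation then gives about 4.3%. The stratified test stays at about 5%.

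**3. Power.** Simulation with about 300 randomised per arm, 20% random loss, equal-sized sites, marginal rates held at 22.0% and 35.4%, and 20,000 trials per setting. The number of sites and the SD are assumptions.

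| Site SD (logit) | Sites | Stratified Mantel-Haenszel | Pooled chi-square | Difference (points) |
|---|---|---|---|---|
| 0 | 10 / 20 | 90.1 / 90.1% | 90.2 / 90.4% | −0.1 / −0.3 |
| 0.3 | 10 / 20 | 90.7 / 90.7% | 90.5 / 90.6% | 0.2 / 0.1 |
| 0.5 | 10 / 20 | 91.6 / 91.3% | 90.9 / 90.6% | 0.7 / 0.7 |
| 0.8 | 10 / 20 | 92.8 / 92.9% | 91.3 / 91.4% | 1.5 / 1.5 |

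A repeat with 60,000 trials per setting gave 1.7 points at SD 0.8 for both site counts (92.8% against 91.1%, and 92.9% against 91.2%). The gain from stratifying alone is therefore 0 to about 1.7 points. At SD 1.0 it was 2.3 to 2.5 points.

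**4. Separating out the Fisher test.** At 239 per arm with no site differences, exact power is 88.5% for Fisher and 90.3% for the pooled chi-square. That gap of 1.8 points exists before site enters, so it is not a cost of pooling.

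**5. Many small sites.** With 60 sites there are 300/60 = 5 randomised and about 4 evaluable patients per arm per site. Unmerged, the stratified test has 89.6% power against 90.5% pooled at SD 0 (a loss of 0.9 points), and 90.1% against 90.6% at SD 0.3. At 100 sites and SD 0 it has 88.8% against 90.5%.

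**The case against.** The strongest reply is that the harm is small and conditional. Both the site count and the SD are assumed. An SD of 0.8 with mean sham response of 22% puts 95% of sites between about 5% and 53%, and nothing in the documents supports a spread that wide. The protocol also makes sites alike: training uses a video and an instruction sheet, every patient completes a practice diary, and both primary outcomes are self-recorded after treatment at home. Pooling avoids sparse strata, and a conservative test does not weaken a positive result. All of this stands and sets the size of the point.

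A reader might go further in four ways that the documents do not support:

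- **That the sites are intended to differ.** Section 4.2 lists recruitment routes and does not assign them to types of site. Differences are plausible, not planned.
- **That arms are exactly balanced within site.** The balance is in the kits shipped. Incomplete last blocks, the unstated order of use, the mITT conditions and the expected loss ("Taking into account a rate of 20% of patient loss during the study") make it approximate.
- **That pooling endangers the planned power.** Pooled chi-square power stays at 90 to 91% throughout the table. What is forgone is a possible gain.
- **That the whole difference between a pooled Fisher test and a stratified test is due to site.** About 2 points of it is Fisher's conservatism.

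The reply does not answer the missing view of consistency across sites. Nor does it show a material cost to stratifying once small sites are merged. An Anova could carry a site factor, but the plan does not say that it will.

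**Conclusion.** The point holds as a modest matter of efficiency and reporting. Allocation is approximately balanced within site and no planned comparison uses site. Under the assumed 10 to 20 equal sites and SD 0 to 0.8, stratifying alone gains 0 to about 1.7 points of power over a pooled chi-square. At SD 0.8 it also brings type I error from about 4% to 5%. If sites do not differ, there is nothing to gain.

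A reader might infer that ignoring site biases the treatment effect or produces false positives. It does not do so materially: the error runs in the conservative direction. Exclusions that differed by arm within sites could disturb the comparison, but the documents give no sign of this, and the calculations assume random loss.

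**What to change.** In section 8.2.3, state that the two primary outcomes and the yes/no secondary outcomes are compared with a Mantel-Haenszel test stratified by investigational site, reported with the stratified risk difference and its 95% confidence interval.

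State a minimum number of mITT patients per site, counted over both arms, and a rule for merging sites below it, both fixed before unblinding. The calculations bracket the choice: about 12 evaluable patients per arm per site (240/20) cost at most 0.3 points, while about 4 (240/60) cost about 1 point when sites differ little.

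Add a descriptive table of both primary outcomes by site and arm, without by-site tests.

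The cost is a few sentences, one standard procedure and one table. Kits are shipped by investigator and their numbers are recorded in the CRF, so no new data are needed. The planned 600 patients can stand. The small downside is the need for the merging rule.
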